[name], MSc Clinical Assistant Professor, Department of Obstetrics and Gynaecology, CHU Sainte-Justine

[name], FRCSC Professeure adjointe de Clinique, Département de pédiatrie, Université de Montréal

Newfoundland & Labrador

[name], MSc, FRCSC Professor, Department of Obstetrics & Gynecology, Memorial University

Nova Scotia

[name], FRCSC Associate Professor, Department of Obstetrics & Gynecology, Dalhousie University; Reproductive Care Program of Nova Scotia

New Brunswick

[name] Medical Director, Perinatal New Brunswick Health Program; Maternal-Fetal Medicine specialist, Horizon Health Network

Prince Edward Island [name]

Obstetrician/Gynecologist, Charlottetown, Prince Edward Island

Yukon

[name], FRCSC Obstetrician-Gynecologist, Whitehorse General Hospital

Northwest Territories [name], FRCSC Adjunct Professor, Territorial Clinical Lead, Women's & Children's Health, Northwest Territories Health and Social Services Association

Nunavut

[name] Obstetrician-Gynecologist, Nunavut

SUMMARY

Title	Canadian COVID-19 Vaccine Registry for Pregnant & Lactating Individuals (COVERED): An Evaluation of Safety, Effectiveness & Acceptability
Goal	Provide a national registry of unvaccinated and vaccinated pregnant and lactating individuals who will be followed to determine data on safety for any of the vaccine types and how well they protect against COVID-19.
Objectives	 Primary objectives: 1. To assess the safety of COVID-19 vaccines in pregnant and lactating individuals 2. To describe the effectiveness of COVID-19 vaccines in pregnant and lactating individuals 3. To examine attitudes towards COVID-19 vaccination, and other vaccines, including RSV, among pregnant and lactating individuals 4. To examine the immunogenicity of COVID-19 vaccines within a subset of pregnant individuals and for their infants 5. To assess attitudes and the impact of co-administration of the COVID-19 vaccine, among pregnant and lactating individuals
Timeline	May 2021March 2024
Project design	Prospective Cohort
Inclusion criteria	 (1) At least 19 years of age (2) Became pregnant in 2023
Data collection and time points Data collection and timepoints for immune sub-study	 Baseline survey administered at start of enrollment 2 time-based follow up surveys administered: December 1st 2023 and February 1st 2024 Reminders to follow up surveys will be sent out periodically throughout study duration Access to previously collected antenatal samples Maternal/gestational parent blood samples will be collected four weeks to up to one day before vaccination, four weeks after vaccination, 12 weeks after vaccination, delivery +/- 2 days, and 4-6 weeks after delivery
	 weeks after delivery. Umbilical Cord blood samples at delivery and infant blood samples and breast milk at 4-6 weeks post delivery

1.0 BACKGROUND

1.1 Epidemiology of SARS-CoV-2

In December 2019, a novel coronavirus, eventually termed Severe Acute Respiratory Syndrome associated Coronavirus-2 (SARS-CoV-2), was identified in Wuhan, China. On March 11, 2020, the WHO declared Coronavirus Disease 19 (COVID-19), the respiratory illness caused by SARS-CoV-2 infection, an official global pandemic. As of April 19, 2021, globally, SARS-CoV-2 has infected >141,000,000 people and caused over 3,000,000 deaths (1). As of April 19, 2021, Canada has 1,131,773 confirmed cases and 23,667 deaths, with cases occurring in individuals returning from international travel or their close contacts and via extensive community spread (2).

Pregnant women and individuals are a key population for COVID-19 prevention due to increased risk of hospitalization and ICU admission (3-5). Rapid evaluation of COVID-19 vaccination in this population is therefore imperative. Building upon the established national expert network CANCOVID-Preg, our team is well positioned to conduct vaccine evaluation in this important population.

1.2 Study Rationale

There have been no formal trials of approved or candidate vaccines in pregnancy to date and as such, there will not be adequate data in pregnancy, and particularly among pregnant individuals with comorbidities, for the foreseeable future. Priority groups to receive the vaccine initially included health care workers, a large proportion of whom are reproductive age females. In recent weeks, many provinces have moved to offering vaccines to all pregnant people based on the data from our other project, CANCOVID-Preg (https://ridprogram.med.ubc.ca/cancovid-preg/) that has shown that hospitalization and ICU admission rates for pregnant individuals are equivalent to the age grouping of 55-59 in the general population. The National Advisory Committee on Immunizations (NACI), Society of Obstetricians and Gynaecologists of Canada (SOGC), American College of Obstetrics & Gynecology (ACOG), and other national and international organizations have endorsed vaccinations being made available to pregnant women and for them to make an informed decision on whether to take that opportunity (6-8). Data on the use of COVID-19 vaccines in this population is limited to an initial v-safe report (9) resulting in a major knowledge gap in the roll out of vaccine in Canada and globally, which may contribute to decreased vaccine confidence in this population which historically experiences lower vaccine confidence (10). This project will use a prospective cohort design in conjunction with both traditional and social media campaigns to capture data on the safety, effectiveness, and immunogenicity of COVID-19 vaccines in pregnant or lactating individuals.

1.3 Immune Sub-Study

Participants in BC, who have access to a study site or the ability to provide study samples, and who intend to receive a COVID-19 vaccine during pregnancy, will be offered the option of participating in an immune sub-study. Consent will be obtained to access previously collected antenatal serology and the prospective collecting of parent and infant blood for serological assessment. Initial engagement has been established at two BC sites; BC Women's Hospital and Surrey Memorial Hospital with the potential of additional sites throughout BC.

2.0 OBJECTIVES

Primary objectives:

1. To assess the safety of COVID-19 vaccines in pregnant and lactating individuals

2. To describe the effectiveness of COVID-19 vaccines in pregnant and lactating individuals

3. To examine attitudes towards COVID-19 vaccination, and other vaccinations, including RSV, among pregnant and lactating individuals

4. To examine the immunogenicity of COVID-19 vaccines within a subset of pregnant individuals and for their infants

5. To assess attitudes and the impact of co-administration of the COVID-19 vaccine with other regular vaccinations, such as the influenza vaccine, among pregnant and lactating individuals

3.0 STUDY DESIGN

3.1 Study Design

Objectives will be addressed using a prospective cohort design. A public campaign will be launched to invite pregnant and lactating women and individuals to participate in online surveys with self-reported outcomes. This methodology has been modeled after U.S. efforts led by the University of Washington (11). The project will provide the Public Health Agency of Canada (PHAC), NACI, and provincial vaccine advisory committees with Canadian data to guide recommendations as the study rolls out. This project will be leveraging the national CANCOVID-Preg network and existing collaborations with public health partners.

3.2 Inclusion Criteria

- (1) At least 19 years of age
- (2) Became pregnant in 2023

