4.2 Data Collection

Once consent has been obtained, the baseline survey will automatically be pushed to the participant. The baseline answers will determine if pregnancy and or vaccine outcome surveys are to be answered at the same time. A short follow-up questionnaire will be administered on December 1st 2023 and another on February 1st 2024 to capture changes in vaccination status, COVID-19 status, pregnancy outcomes or significant health events. The follow-up surveys will determine if/when outcome surveys need to be completed. If consent is withdrawn, the study will immediately cease for the participant. The survey modules are as follows:

1. Baseline survey: Pregnancy status, vaccination status, demographics, health history, COVID-19 history & pregnancy history - Administered at enrollment starting Sept 1, 2023 until Jan 31, 2024

2. Pregnancy Outcomes: Pregnancy & infant outcomes – Administered if pregnancy started in 2023 and are not currently pregnant

3. Vaccine Outcomes: Answered if a dose of a COVID-19 vaccine received during the current pregnancy

4. Vaccine Attitudes 1: Feelings, opinions & attitudes towards vaccines– Administered at end of surveys received at baseline

5. Vaccine Attitudes 2: Feelings, opinions, and attitudes towards the Respiratory syncytial virus (RSV) – Administered following the completion of Vaccine Attitudes 1

6. Follow-up survey: 2 time-based follow-up surveys administered on December 1st, 2023, and on February 1st, 2024 with reminders sent out periodically throughout study duration
7. Health Event: Significant health events resulting in a visit to the emergency department or hospitalization – Administered if triggered by Follow-up survey

In the event of an adverse reaction or major health event, the study team will contact a participant for further health information.

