Data collected from individuals who do not receive COVID-19 vaccines will act as an internal comparison group. We will also capture self-identified gender through our online demographics questionnaire and examine differences by gender. The module on COVID-19 vaccination history will include type of vaccine received, number of doses and dosing interval. Vaccine safety endpoints will be coordinated with the Canadian National Vaccine Safety Network (CANVAS) endpoints: adverse events as detailed in data collection forms, severity and duration of adverse event, resultant medical visits (including to emergency department) or hospitalization, and treatments administered.

Pregnancy and infant safety outcomes measured are key outcomes identified by the Pan-Canadian, surveillance CANCOVID-Preg team. These major pregnancy complications/outcomes include but are not limited to gestational hypertension, gestational diabetes, placental abruption, infant birthweight, preterm birth, NICU admission, congenital anomalies, spontaneous abortion or termination, and stillbirth or neonatal death. Postnatally, including infants of women vaccinated during lactation, infant SARS-CoV-2 infection, hospitalization, growth parameters, and neurodevelopment (hyper vigilance) will be ascertained.

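### The objectives cover lactating individuals in general, but entry by a 2023 pregnancy start limits the lactating group to roughly the first four to five months after a term birth

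*Protocol*

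**What the plan says.** **Target population.** Section 2.0 sets as objective 1 "To assess the safety of COVID-19 vaccines in pregnant and lactating individuals" and as objective 2 "To describe the effectiveness of COVID-19 vaccines in pregnant and lactating individuals". Objectives 3 (attitudes) and 5 (co-administration) name the same two groups; objective 4 (immunogenicity) names only pregnant individuals and their infants. The title and goal in the Summary also include lactating people. Section 3.1 states: "A public campaign will be launched to invite pregnant and lactating women and individuals to participate in online surveys with self-reported outcomes". Section 4.2 promises infant outcomes after vaccination in lactation: "Postnatally, including infants of women vaccinated during lactation, infant SARS-CoV-2 infection, hospitalization, growth parameters, and neurodevelopment (hyper vigilance) will be ascertained".

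**Entry.** Section 3.2, like the Summary, has two criteria: an age of at least 19 and "2) Became pregnant in 2023". Neither admits a person because they are lactating.

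**Dates.** Section 4.2 describes the baseline survey as "Administered at enrollment starting Sept 1, 2023 until Jan 31, 2024" and follow-up as "2 time-based follow-up surveys administered on December 1st, 2023, and on February 1st, 2024".

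**Survey modules (section 4.2).** Pregnancy Outcomes goes to people whose pregnancy started in 2023 and has ended. Vaccine Outcomes is answered only for a dose received in the current pregnancy. The two attitude modules follow the baseline surveys and carry no restriction by pregnancy status.

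**The concern.** The population named in four of the five primary objectives is wider than the one the criteria admit. A person breastfeeding an infant from a 2022 pregnancy belongs to the stated target but cannot enter. Those who can enter as lactating are all in the early months after birth.

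The registry is meant to supply federal and provincial vaccine advisory bodies with data to guide recommendations (section 3.1) and to issue monthly public reports (section 4.7). Safety, effectiveness or attitude statements worded for lactating individuals would rest on early lactation alone. No later analysis can recover people who were never eligible.

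**Working it through.** The protocol states no figure for lactating participants, so there is none to reproduce. The check is calendar arithmetic.

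**Inputs from the protocol:** pregnancy start from 1 January 2023 (section 3.2); enrolment from 1 September 2023 to 31 January 2024, which is 153 days; last scheduled survey 1 February 2024 (section 4.2).

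**Assumptions, not in the protocol:** time from pregnancy start to term birth, g, of 245 days (dated from conception, 37 weeks) to 280 days (dated from last menstrual period, 40 weeks); births spread evenly; one common lactation length L, with a month of 30.44 days. Preterm births are left out, as are people still nursing an older child who conceived again in 2023.

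**Step 1: earliest eligible term birth and oldest infant.** Earliest birth = 1 January 2023 + g.

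| Dating and delivery | g (days) | Earliest birth | Oldest infant, 31 Jan 2024 | Oldest infant, 1 Feb 2024 |
|---|---|---|---|---|
| Conception, 37 weeks | 245 | 3 Sept 2023 | 150 days | 151 days |
| Last period, 37 weeks | 259 | 17 Sept 2023 | 136 days | 137 days |
| Conception, 40 weeks | 266 | 24 Sept 2023 | 129 days | 130 days |
| Last period, 40 weeks | 280 | 8 Oct 2023 | 115 days | 116 days |

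From 1 September until the earliest birth there are 2 to 37 enrolment days on which nobody lactating after a term birth of an eligible pregnancy can exist (23 days for g = 266).

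**Step 2: average eligible share over the window.** On day t the share is min(days since earliest birth, L) / L, set to 0 before the earliest birth and averaged over 153 days. Worked for g = 266, where the count runs from 1 to 129:

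- Sum of days = 129 × 130 / 2 = 8,385, and 8,385 / 153 = 54.8 days on average.
- L = 12 months: 54.8 / 365.3 = 15%.
- L = 6 months: 54.8 / 182.6 = 30%.
- L = 3 months (91.3 days, so the count is capped): (91 × 92 / 2 + 38 × 91.3) / 153 = 50.0 days, and 50.0 / 91.3 = 55%.

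| Lactation length L | g = 280 | g = 266 | g = 245 |
|---|---|---|---|
| 3 months | 46% | 55% | 69% |
| 4 months | 36% | 45% | 59% |
| 6 months | 24% | 30% | 41% |
| 12 months | 12% | 15% | 20% |
| 24 months | 6% | 8% | 10% |

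**Step 3: last enrolment day.** The share rises through the window. On 31 January 2024 it is 115/182.6 = 63%, 129/182.6 = 71% and 150/182.6 = 82% for L = 6 months (g = 280, 266, 245), and 32%, 35% and 41% for L = 12 months.

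**Step 4: entry while pregnant.** People enrolled in pregnancy may be lactating by a follow-up survey. With pregnancy starts spread evenly over 2023, the share reaching term by 31 January 2024 is 115/365 = 32% to 150/365 = 41% (35% for g = 266). This route adds early-lactation participants. It brings in nobody whose pregnancy began before 2023.

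**Step 5: modules.** A dose given during lactation does not trigger Vaccine Outcomes. A person admitted only as lactating from a 2022 pregnancy would trigger neither that module nor Pregnancy Outcomes.

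**The case against.** The strongest reply is that the lactation objectives are still served. A reader might infer from the mismatch that they cannot be answered at all, and the protocol does not support that. People who have delivered a 2023 pregnancy can enrol, and pregnant participants can begin lactating before the December or February survey. The attitude modules reach postpartum entrants, the follow-up surveys record vaccination and COVID-19 status, and section 4.5 plans effectiveness only descriptively. Objectives 2 and 3 can therefore be addressed for early lactation. This stands.

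A reader might also infer that most lactating people are shut out, as a matter of fact. That depends on a lactation length the protocol does not give. On average over the window it holds at 6 months or longer for every g tested, is borderline at 3 to 4 months, and fails for shorter lactation. Even at 6 months, most are eligible on the last enrolment day (step 3).

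Three further points:

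- The Summary's timeline starts in May 2021, so earlier enrolment under other criteria is possible. The protocol describes no such cohort and no plan to pool one.
- Section 4.1 lists La Leche League as a way to reach a diverse population and ties recruitment to the inclusion criteria. It is not separate evidence of a wider lactating target, and the point does not need it.
- The pregnancy comparisons and the sample sizes in section 4.5 are unaffected. This bears on severity and stands.

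None of these replies admits a person lactating from an earlier pregnancy, so the mismatch remains.

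**Conclusion.** The mismatch is real, in a limited form. Eligibility and objectives 1, 2, 3 and 5 do not describe the same lactating population. The protocol can inform on roughly the first four to five months after a term birth, with few or no eligible lactating people in the first weeks of enrolment. It cannot support conclusions about lactating individuals overall.

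The exclusion and the age limit follow from the protocol's dates and an assumed 37- to 40-week delivery. The age limit refers to the scheduled survey date; a February survey completed as late as 31 March 2024, the end of the timeline, would raise it to 175 to 210 days without changing who may enter. The eligible shares are illustrations that also rest on evenly spread births and an assumed lactation length.

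Severity: should-fix. The pregnancy analyses stand, and a change of wording is enough.

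**What to change.** **Preferred: narrow the claim.** In the title, the goal, objectives 1, 2, 3 and 5 and every reported statement on lactation, limit the lactating group to early-postpartum participants whose pregnancy began in 2023. The cost is wording only; the downside is a narrower claim.

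**If the sponsor wants the wider population:**

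1. Add 'OR lactating at enrolment' to criterion 2 in both the Summary and section 3.2.
2. In section 4.2, extend the Vaccine Outcomes trigger to doses received during lactation, and extend infant-outcome collection to these entrants. Without this step they would receive neither outcome module (step 5).
3. Report them as a separate cohort, and keep the pregnancy-outcome comparison to pregnancies begun in 2023.

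This costs an amendment to the criteria, changes to the survey logic and a separate set of results. It is more than a one-line edit.

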4.0 PROTOCOL

4.1 Recruitment

Vaccinated and unvaccinated women and individuals will be invited to participate in a voluntary web-based surveillance. They will be followed prospectively as a cohort to collect data on attitudes and outcomes associated with vaccination. Recruitment will be targeted based on the inclusion criteria, regardless of vaccination status or intention. Recruitment will occur through a social media and traditional media campaign and through dissemination of recruitment materials by health care providers. The study will have a UBC supported website that will contain information as well as a link that for individuals to be directed to the study e-consent. Once the research data base is built, the link will route potentially interested participants to the study information and consent. For those individuals that expressed an interest in the study, the study team will send the website information once ethics approval has been obtained. We plan to engage with physicians, midwives, The Society of Obstetricians & Gynaecologists of Canada, Black Physicians of Canada, Indigenous Physicians Association of Canada, and La Leche League to reach a diverse study population. We plan to recruit from local maternity, family medicine, and midwifery clinics, like Pomegranate and the Vancouver Family Practice Centre, as well as on the REACH BC website. We will also engage with the Oak Tree Clinic and the Maternal Fetal Medicine Clinic at BC Women's Hospital. We plan to implement a poster campaign with QR codes as well as utilize social media posts to share the study website using Instagram, Facebook and Twitter. Study postcards will be distributed that contain the

inclusion criteria, study objectives and a QR code that will take a potential participant to the registry e-consent. As demographic data are collected from participants in the baseline survey, our team will be able to rapidly adjust the media campaign to target areas of the country or populations with lower enrollment.

4.2 Data Collection

Once consent has been obtained, the baseline survey will automatically be pushed to the participant. The baseline answers will determine if pregnancy and or vaccine outcome surveys are to be answered at the same time. A short follow-up questionnaire will be administered on December 1st 2023 and another on February 1st 2024 to capture changes in vaccination status, COVID-19 status, pregnancy outcomes or significant health events. The follow-up surveys will determine if/when outcome surveys need to be completed. If consent is withdrawn, the study will immediately cease for the participant. The survey modules are as follows:

1. Baseline survey: Pregnancy status, vaccination status, demographics, health history, COVID-19 history & pregnancy history - Administered at enrollment starting Sept 1, 2023 until Jan 31, 2024

2. Pregnancy Outcomes: Pregnancy & infant outcomes – Administered if pregnancy started in 2023 and are not currently pregnant

3. Vaccine Outcomes: Answered if a dose of a COVID-19 vaccine received during the current pregnancy

4. Vaccine Attitudes 1: Feelings, opinions & attitudes towards vaccines– Administered at end of surveys received at baseline

5. Vaccine Attitudes 2: Feelings, opinions, and attitudes towards the Respiratory syncytial virus (RSV) – Administered following the completion of Vaccine Attitudes 1

6. Follow-up survey: 2 time-based follow-up surveys administered on December 1st, 2023, and on February 1st, 2024 with reminders sent out periodically throughout study duration
7. Health Event: Significant health events resulting in a visit to the emergency department or hospitalization – Administered if triggered by Follow-up survey

In the event of an adverse reaction or major health event, the study team will contact a participant for further health information.

Data collected from individuals who do not receive COVID-19 vaccines will act as an internal comparison group. We will also capture self-identified gender through our online demographics questionnaire and examine differences by gender. The module on COVID-19 vaccination history will include type of vaccine received, number of doses and dosing interval. Vaccine safety endpoints will be coordinated with the Canadian National Vaccine Safety Network (CANVAS) endpoints: adverse events as detailed in data collection forms, severity and duration of adverse event, resultant medical visits (including to emergency department) or hospitalization, and treatments administered.

Pregnancy and infant safety outcomes measured are key outcomes identified by the Pan-Canadian, surveillance CANCOVID-Preg team. These major pregnancy complications/outcomes include but are not limited to gestational hypertension, gestational diabetes, placental abruption, infant birthweight, preterm birth, NICU admission, congenital anomalies, spontaneous abortion or termination, and stillbirth or neonatal death. Postnatally, including infants of women vaccinated during lactation, infant SARS-CoV-2 infection, hospitalization, growth parameters, and neurodevelopment (hyper vigilance) will be ascertained.

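### The last outcome contact is a fixed date, 1 February 2024, although any pregnancy begun in 2023 is eligible; delivery and infant outcomes go uncollected for a large share, and recorded endings tilt early

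*Protocol*

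**What the plan says.** Eligibility (Protocol 3.2) is age 19 or over and "Became pregnant in 2023". The baseline survey is "Administered at enrollment starting Sept 1, 2023 until Jan 31, 2024" (4.2). After baseline, "A short follow-up questionnaire will be administered on December 1st 2023 and another on February 1st 2024" (4.2). The list of survey modules in the same section repeats this as "2 time-based follow-up surveys administered on December 1st, 2023, and on February 1st, 2024 with reminders sent out periodically throughout study duration".

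The Pregnancy Outcomes module, which carries the infant outcomes, is "Administered if pregnancy started in 2023 and are not currently pregnant" (4.2). Its trigger is the baseline survey or a dated follow-up: "The follow-up surveys will determine if/when outcome surveys need to be completed" (4.2). The timeline in the Summary reads "May 2021March 2024".

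Section 4.2 lists birthweight, preterm birth, NICU admission, congenital anomalies, pregnancy loss, stillbirth and neonatal death among the safety outcomes. For the postnatal period it adds infant infection, hospitalisation, "growth parameters, and neurodevelopment (hyper vigilance) will be ascertained". Section 4.5 gives 500 per group, 80% power and a minimum relative risk of 1.5 for the vaccinated versus unvaccinated comparison, and plans time-varying Cox models.

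**The concern.** A pregnancy lasts about nine months, and the eligibility window is a full year that closes one month before the last survey. A participant still pregnant when she answers the February survey does not qualify for the outcome module then, and no later survey is named that would trigger it. Her delivery and infant outcomes are then never recorded. No analysis plan can supply data that were not collected.

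Two things are at stake for the first primary objective, safety. The number evaluable for delivery and infant outcomes is well below the number enrolled. And the endings that are recorded are not a fair sample: an early loss has a longer calendar window in which to be recorded than a term birth, so crude proportions of loss and preterm birth come out too high.

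**Working it through.** **Inputs from the protocol.** Pregnancy starts 1 January to 31 December 2023 (365 days); enrolment 1 September 2023 to 31 January 2024; last survey 1 February 2024; timeline end March 2024, taken as 31 March; 500 per group, 80% power, relative risk 1.5.

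**Assumptions.** Starts spread evenly over 2023. The due date is 280 days after the start if pregnancy is counted from the last menstrual period (LMP), or 266 days if counted from conception; the protocol does not say which. Two-sided alpha 0.05.

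**1. The plan's own figure.** Section 4.5 gives no baseline risk, so its 80% cannot be strictly reproduced. With 500 per group and relative risk 1.5, a two-proportion test has power 0.372 at a 5% risk, 0.667 at 10% and 0.796 at 13%. A risk near 13% is therefore what 80% implies.

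**2. Eligible pregnancies not yet due.** Last start date that is due in time = cut-off minus 280 or 266 days.

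| Cut-off | Dating | Last start due in time | Due by cut-off | Not yet due |
|---|---|---|---|---|
| 1 Feb 2024 | LMP | 27 Apr 2023 | 117/365 = 32.1% | 67.9% |
| 1 Feb 2024 | Conception | 11 May 2023 | 131/365 = 35.9% | 64.1% |
| 31 Mar 2024 | LMP | 25 Jun 2023 | 176/365 = 48.2% | 51.8% |
| 31 Mar 2024 | Conception | 9 Jul 2023 | 190/365 = 52.1% | 47.9% |

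At 37 weeks rather than the due date, the 1 February cut-offs are 18 May (LMP; 138/365 = 37.8%) and 1 June 2023 (conception; 152/365 = 41.6%), so 58-62% have not reached 37 weeks. The last eligible pregnancies, begun 31 December 2023, are due 22 September to 6 October 2024.

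**3. People who could enrol.** Simulated with a uniform enrolment date, at least 3 weeks after conception, and conception dating. Not yet due at 1 February: 56% if people whose pregnancy has already ended also join, 69% if only those still pregnant join. At 31 March: 37% and 45%. Not yet at 37 weeks on 1 February: 49% and 60%.

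**4. Tilt of recorded endings.** Illustrative true values: 12% loss (at 6-14 weeks) and 8% preterm among births, with no selection at enrolment. Among pregnancies ended by 1 February, 25% are losses; among recorded births, 10% are preterm; 38% of all births are recorded. With capture to 31 March the figures are 20%, 9.5% and 54%. Restricting the same simulation to pregnancies due by 1 February gives 12% losses and 8% preterm, so the restriction removes this tilt.

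**5. Evaluable number and power.** 500 × 0.321 = 160 and 500 × 0.359 = 180 at 1 February; 500 × 0.482 = 241 and 500 × 0.521 = 260 at 31 March. With risk 13% versus 19.5%, two-proportion power is 0.35 at 160, 0.39 at 180, 0.49 at 240 and 0.52 at 260.

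**6. Infant age.** From a conception on 1 January 2023, a birth on its due date falls on 24 September 2023, 130 days (about 4 months) before 1 February 2024. A 37-week birth falls on 3 September, 151 days (about 5 months) before it.

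**The case against.** The strongest reply is that 1 February is a send date, not a stated closing date. Reminders run through the study, the timeline goes to March 2024, and the follow-up survey settles when outcome surveys are due, so some later births may be reported. This stands in part: the text allows such reports but fixes no contact that would obtain them, and full capture to 31 March still leaves 37-45% of enrolled pregnancies not yet due. For the same reason, someone enrolled on 31 January cannot be said to be followed for exactly one day.

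Second, the enrolled cohort is not the eligible population. Outcome surveys can be answered together with baseline, and a breastfeeding organisation is among the recruitment channels (4.1), so already-ended pregnancies will enter. A reader might infer that two thirds of the cohort, or most of it in every case, lack birth outcomes. The documents do not support that: the two-thirds figure is for eligible pregnancies, and the enrolled share drops below half if replies run to 31 March.

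Third, a reader might infer that only losses and preterm births can be recorded for conceptions after 11 May 2023. That confuses the due date with term. Births at 37 weeks or later can be recorded for conceptions up to 1 June.

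Fourth, the Cox model censors ongoing pregnancies, which lessens bias for loss and preterm birth if time is gestational and entry is delayed. That stands, and such detail may be in an analysis plan not shown. Censoring cannot supply birthweight, NICU admission, anomalies or neonatal outcomes.

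Fifth, a reader might take 35-39% as the plan's true power. It is not: the 13% risk is back-solved, 500 per group is a condition and not an enrolment cap, and a two-proportion test is not the planned analysis.

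Finally, a reader might extend the point to about half of the immune sub-study's delivery samples. Section 4.3 ties those samples to delivery without a calendar stop, and participants are people in British Columbia who intend to be vaccinated (1.3), so an even-2023 extrapolation has no basis there.

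**Conclusion.** The concern holds. As written, the schedule leaves delivery and infant outcomes uncollected for a large share of participants: about 56-69% of those able to enrol are not yet due at 1 February 2024, or 37-45% if replies are captured to 31 March. These ranges rest on even starts over 2023 and a uniform enrolment date, and their width reflects who joins. Crude proportions among recorded endings are too high for loss and preterm birth, about 25% against 12% and 10% against 8% under the illustrative values. Fewer early losses among those who enrol would reduce the first figure.

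The 500 per group cannot be read as the evaluable number for delivery and infant outcomes. The power figures show the size of the loss only if the stated 80% rests on a baseline risk near 13%. Growth and neurodevelopment can be observed only in early infancy.

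**What to change.** In sections 4.2 and 4.5:

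- State the date of the last outcome contact, and state that delivery and infant outcomes are analysed only in pregnancies whose due date falls on or before it, whatever the actual ending date.
- For loss and preterm birth, use gestational time with delayed entry and censor ongoing pregnancies.
- Restate the evaluable number per group and the detectable relative risk, naming the baseline risk.
- Limit growth and neurodevelopment claims to the infant ages observed, about 4 months at 1 February for the earliest due-date birth and about 5 months for a 37-week birth.

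This costs analysis wording and a smaller stated number. It needs no new data collection.

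Optionally, if the end date can move, add an automatic REDCap outcome survey after each participant's due date. At due date plus 6 weeks, the last would go out in November 2024 (22 September to 6 October plus 42 days). That needs a protocol amendment and puts the final report about eight months later, but it collects the missing outcomes and does not merely exclude those pregnancies.
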